4.5.1. Cohort A Primary Efficacy Variable

The primary efficacy variable in Cohort A is:

- Proportion of subjects who have a symptomatic RT-qPCR confirmed SARS-CoV-2 infection (broad-term) during the EAP

A symptomatic RT-qPCR confirmed SARS-CoV-2 infection during the EAP will be any positive post-baseline RT-qPCR obtained during the EAP in which the subject experiences COVID-19 related signs or symptoms within 14 days of a positive test.

4.5.2. Cohort A Key Secondary Efficacy Variables

The key secondary efficacy variables listed below include two types of variables: binary (B) and continuous (C) variables.

Key Secondary Efficacy Variables	Type	Cohort A
Proportion of subjects with viral load >4 (log ₁₀ copies/mL) in NP swab samples during the EAP	B	X
Number of weeks of symptomatic RT-qPCR confirmed SARS-CoV-2 infection (broad-term) during the EAP	C	X
Number of weeks of high viral load >4 (log ₁₀ copies/mL) in NP swab samples during the EAP	C	X
Number of weeks of RT-qPCR confirmed SARS-CoV-2 infection (regardless of symptoms) during the EAP	C	X
Proportion of subjects who have a RT-qPCR confirmed SARS-CoV-2 infection (regardless of symptoms) during the EAP	B	X
Proportion of subjects in placebo group with a RT-qPCR confirmed SARS-CoV-2 infection during the EAP with an index case participating in Study R10933-10987-COV-2067 (comparison of those whose index cases receive REGN10933+REGN10987 vs placebo in Study R1033-10987-COV-2067)	C	X

Duration of symptomatic infection (weeks) is defined as (the end date of all symptoms minus the date of the first symptom+1)/7, where a symptom is defined in Section 4.5. If the symptom is ongoing at the time of the first step analysis, the end date of the symptom will be set as the cutoff date for the first step analysis.

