1.2.2. Secondary Objectives

Cohort A and Cohort A1

The following secondary objectives are for subjects who are seronegative at baseline (based on central lab test) unless stated otherwise.

- To evaluate the efficacy of REGN10933+REGN10987 compared to placebo in preventing a SARS-CoV-2 infection with a high viral load (i.e. viral load >4 (log₁₀ copies/mL))
- To evaluate the impact of REGN10933+REGN10987 compared to placebo on the duration of signs and symptoms in subjects with symptomatic SARS-CoV-2 infection (broad-term) confirmed by RT-qPCR
- To evaluate the impact of REGN10933+REGN10987 compared to placebo on the duration of SARS-CoV-2 infection with a high viral load (i.e. viral load >4 (log₁₀ copies/mL))
- To evaluate the impact of REGN10933+REGN10987 compared to placebo on the duration of SARS-CoV-2 infection
- To evaluate the efficacy of REGN10933+REGN10987 compared to placebo in preventing asymptomatic or symptomatic SARS-CoV-2 infection confirmed by RT-qPCR
- To evaluate the impact of treating the index case with REGN10933+REGN10987 on the incidence of SARS-CoV-2 infection among their household contacts in placebo group (note: This is a cross-study analysis based on only subjects in placebo group of R10933-10987-COV-2069 whose index cases participated in R10933-10987-COV-2067)

- To evaluate the efficacy of REGN10933+REGN10987 compared to placebo in preventing symptomatic SARS-CoV-2 infection (Centers for Disease Control and Prevention (CDC) definition) confirmed by RT-qPCR
- To evaluate the efficacy of REGN10933+REGN10987 compared to placebo in preventing symptomatic SARS-CoV-2 infection (strict-term) confirmed by RT-qPCR
- To evaluate the impact of REGN10933+REGN10987 compared to placebo on SARS-CoV-2 RT-qPCR viral load
- To evaluate the impact of REGN10933+REGN10987 compared to placebo on SARS-CoV-2 infection:
 - On health care utilization
 - On absenteeism from daily responsibilities (where applicable)
- To evaluate the impact of treating any SARS-CoV-2 RT-qPCR positive household member with REGN10933+REGN10987 on the incidence of SARS-CoV-2 infection among their household contacts in placebo group (note: This is a cross-study analysis based on only subjects in placebo group of R10933-10987-COV-2069 whose index or other household member participated in R10933-10987-COV-2067 or in cohort B)
- To characterize the drug concentration-time profiles of REGN10933 and REGN10987 in serum and selected PK parameters

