5.7.2. Adjustment for Multiple Comparison

The overall type I error will be controlled in each of seronegative mFAS-A and seronegative mFAS-B independently at 2-sided 5% significance level.

Seronegative mFAS-A Subjects

The overall type I error will be controlled for the primary hypothesis in Cohort A based on a 2-sided test at an alpha level of 0.05 as follows:

H0: There is no treatment difference between REGN10933+REGN10987 and placebo in the proportion of subjects with a symptomatic RT-qPCR confirmed SARS-CoV-2 infection during the EAP.

H1: There is a treatment difference between REGN10933+REGN10987 and placebo in the proportion of subjects with a symptomatic RT-qPCR confirmed SARS-CoV-2 infection during the EAP

If the primary efficacy endpoint in Cohort A is statistically significant, the alpha level of 0.05 will be released for the key secondary endpoints in Cohort A. The hierarchy testing sequence of key secondary endpoints is presented in the following table.

Table 2: Hierarchy Testing Sequence of Key Secondary Efficacy Endpoints in Seronegative mFAS-A

Key Secondary Efficacy Variables
Proportion of subjects with viral load >4 (log10 copies/mL) in NP swab samples during the EAP
Number of weeks of symptomatic RT-qPCR confirmed SARS-CoV-2 infection (broad-term) during the EAP
Number of weeks of high-viral load >4 (log10 copies/mL) in NP swab samples during the EAP
Number of weeks of RT-qPCR confirmed SARS-CoV-2 infection (regardless of symptoms) during the EAP
Proportion of subjects who have a RT-qPCR confirmed SARS-CoV-2 infection (regardless of symptoms) during the EAP
Proportion of subjects in placebo group with a RT-qPCR confirmed SARS-CoV-2 infection during the EAP with an index case participating in study R10933-10987-COV-2067 (comparison of those whose index cases receive REGN10933+REGN10987 vs placebo in R10933-10987-COV-2067)

Seronegative mFAS-B Subjects

The overall type I error will be controlled for the primary hypothesis in Cohort B based on a 2-sided test at an alpha level of 0.05 as follows:

H0: There is no treatment difference between REGN10933+REGN10987 and placebo in the proportion of subjects who subsequently develop signs and symptoms (broad-term) within 14 days of a positive RT-qPCR at baseline or during the EAP

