For continuous key secondary endpoints in Cohort A and Cohort B (e.g., number of weeks of high viral load >4 (\log_{10} copies/mL) in NP swab samples and number of weeks of symptomatic RT-qPCR-confirmed SARS-CoV-2 infection (broad-term) during the EAP, etc.), visits with missing viral load regardless of symptoms and visits with missing RT-qPCR that do not have any broad-term symptoms within 14 days will not be considered as meeting these endpoint criteria, respectively. For endpoints regarding viral load, only subjects with at least one post-baseline data

will be included in the analysis. These endpoints will be analyzed by the non-parametric method, a stratified Wilcoxon rank sum test (Van Elteren Test) with the region and age group. Descriptive statistics will be provided for number (%) of subjects with each interval of duration in weeks (i.e., 0 week, > 0 to \leq 1 week, > 1 to \leq 2 weeks, etc.) within each treatment group. The total weeks of infection and normalized duration (e.g., average duration infection per 1000 subjects) per treatment group will also be reported.

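### Should cohort A's weeks of symptomatic infection stop at Day 29 because the endpoint's name refers to the EAP?

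*SAP*

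**What the plan says.** SAP Table 2 (5.7.2) places this endpoint second in the cohort A hierarchy: "Number of weeks of symptomatic RT-qPCR confirmed SARS-CoV-2 infection (broad-term) during the EAP". Protocol 4.1.2 uses the same name. The only derivation is under the table in SAP 4.5.2: "Duration of symptomatic infection (weeks) is defined as (the end date of all symptoms minus the date of the first symptom+1)/7". For a symptom still ongoing at the first-step analysis, "the end date of the symptom will be set as the cutoff date for the first step analysis".

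Four other places bear on how the name should be read:

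- SAP 4.5.1, on the primary variable: "A symptomatic RT-qPCR confirmed SARS-CoV-2 infection during the EAP will be any positive post-baseline RT-qPCR obtained during the EAP", with symptoms within 14 days of a positive test.
- SAP 1.2.2, the matching objective: "duration of signs and symptoms in subjects with symptomatic SARS-CoV-2 infection (broad-term) confirmed by RT-qPCR". It sets no time limit.
- SAP 4.5.6, the parallel cohort B endpoint, where the reference to baseline or the EAP is attached to the positive test.
- Protocol 9.1.1, footnote 15, which has sites ask about symptoms every week until they clear, including after the EAP.

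SAP 5.7.3 tests the endpoint with a Van Elteren test. For description it adds duration categories and states: "The total weeks of infection and normalized duration (e.g., average duration infection per 1000 subjects) per treatment group will also be reported".

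**The concern.** Taken alone, the name says that weeks are counted within Day 1 to 29, which allows at most 29/7 = 4.14 weeks. The formula has no such limit. Symptoms are followed past Day 29, and a qualifying onset can fall as late as Day 43 (a positive on Day 29 plus 14 days), so days outside the EAP will be in the data.

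Some drafting supports the narrower reading. The next key secondary counts high viral load "in NP swab samples during the EAP", which limits the samples counted. The missing-data rule in SAP 5.7.3 works by visit: "visits with missing RT-qPCR that do not have any broad-term symptoms within 14 days will not be considered as meeting these endpoint criteria". Elsewhere the SAP writes of an onset in the EAP when it means only onset, and the viral-load AUC states openly that tests after the EAP are used.

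If the name governed, the duration categories, total weeks and weeks per 1000 subjects would include days that do not belong to the endpoint. There would also be two candidate numbers under one label in a tested position.

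**Working it through.** **Which reading fits the text**

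1. The name counts weeks of a symptomatic confirmed infection during the EAP. SAP 4.5.1 defines that infection by a positive test obtained in the EAP. On that definition the qualifier dates the test.
2. The first-step lock comes after all subjects complete the EAP (SAP 7), so the cutoff cannot precede anyone's Day 29. A rule closing ongoing symptoms at the cutoff would have nothing to do under a Day 29 cap. It makes sense only if later days count.
3. The unbounded objective, the follow-up of symptoms until they clear, and the cohort B wording all agree with the formula.

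**Inputs for size**

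Neither document gives an expected value for this endpoint, so there is no figure to reproduce. The borrowed design inputs do check:

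- 1248/(0.9 × 0.7) = 1981, against 1980 stated.
- Odds ratio (0.05/0.95)/(0.10/0.90) = 0.474, against 0.47.
- Power at 624 per arm, 10% vs 5%, is 0.919, against 0.914 in SAP Table 1 at correlation 0.1.

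Symptom duration is 11.5 ± 5.7 days (Protocol 3.2.1), modelled as gamma. Three things are assumed: the onset patterns, uniform entry from 1 Oct 2020 to 28 Jan 2021, and a cutoff of 25 Feb 2021 (28 Jan plus 28 days).

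**Formulas**

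- As written: (min(end, cutoff) − onset + 1)/7
- Capped: max(0, min(end, Day 29) − onset + 1)/7

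For a 12-day episode:

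- Onset Day 5: 1.71 weeks both ways.
- Onset Day 22: 1.71 as written, 1.14 capped.
- Onset Day 43: 1.71 as written, 0 capped.

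**Mean weeks per symptomatic subject (1,000,000 draws per pattern)**

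| Onset pattern | As written | Capped | Ratio | Subjects with days past Day 29 |
|---|---|---|---|---|
| Uniform Day 2–8 | 1.641 | 1.626 | 1.009 | 2.8% |
| Uniform Day 2–15 | 1.641 | 1.592 | 1.031 | 8.3% |
| 75% Day 2–8, 25% Day 9–29 | 1.637 | 1.503 | 1.089 | 15.0% |
| Uniform Day 2–22 | 1.636 | 1.485 | 1.102 | 21.5% |
| Uniform Day 2–29 | 1.622 | 1.251 | 1.296 | 39.1% |

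At 10% symptomatic, placebo weeks per 1000 = 1000 × 0.10 × 1.641 = 164 as written. Capped values for the first two patterns are 163 and 159. With the active arm at 5%, the between-arm difference is 82 as written, against 81 and 80 capped.

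At the 3.6% placebo rate seen in the administrative assessment, with 1.8% assumed on active, the difference is 29.5 as written, against 29.3 and 28.7 capped.

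Of 624 × (0.10 + 0.05) = 93.6 symptomatic subjects, about 1 to 3 change duration category in those two patterns (1.1% and 3.7%). At most about 1 is ongoing at the cutoff in the first four patterns (0.1% to 1.0%).

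Day 8 positivity in the administrative assessment, 10.3% placebo vs 5.4% active (Protocol 3.2.6), makes early onset the more likely case.

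**Effect on the test**

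This used 2,000 simulated trials with an unstratified Wilcoxon test and independent subjects. About 1 − (0.10 + 0.05)/2 = 92.5% of subjects score zero either way.

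| Onset | Power as written | Power capped |
|---|---|---|
| Day 2–15 | 0.936 | 0.936 |
| Day 2–22 | 0.921 | 0.921 |
| Day 2–29 | 0.930 | 0.931 |
| Day 2–43 | 0.926 | 0.783 |

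The last row is extreme, with a third of onsets after Day 29. There the cap loses power, because those subjects are primary events scored as zero weeks.

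**What a cap would measure**

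With onset Day 2–15, delay every onset by 7 days and leave illness length alone. Capped weeks fall from 1.59 to 1.42, about 11%. Weeks as written stay at 1.64. The capped measure would show a shorter illness where there is none.

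**The case for a change.** The strongest case for a change is that a name in a testing hierarchy should not need interpretation. The SAP never says outright that the qualifier dates the test, and it words onset and post-EAP data explicitly in other endpoints. The rationale in the Amendment 6 history also places these durations within the 28-day period. That history describes changes, however, and does not override the SAP's definitions. The visit-based rule in SAP 5.7.3 deals with missing tests and caps no symptom dates. In the viral-load endpoint the phrase attaches to swabs.

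A second objection has more weight. Closing ongoing symptoms at a calendar cutoff makes the value depend on entry date. Take symptoms ongoing from Day 5, with the assumed 25 Feb 2021 cutoff. A subject randomized 28 Jan 2021 scores 3.57 weeks, and one randomized 1 Oct 2020 scores 20.57. Those 17.0 extra weeks in an arm of 624 add 17.0/624 × 1000 = 27 weeks per 1000, which is visible in a descriptive total.

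This stands as a caution in reading the total. It does not reach the rank test in any material way, it applies alike to both randomized arms, and it concerns about one subject or fewer in the first four patterns. The longer value is also a true lower bound on that subject's illness. The planned duration categories, and the symptom listing with start and end dates (SAP 5.8.1), would show such a subject.

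**Conclusion.** No change is needed. The name is loose, but the SAP gives one computable rule, and its definition, objective, cutoff rule and follow-up schedule all support duration to resolution. Following it gives a sound result. Against a Day 29 cap, mean weeks differ by about 1% to 3% with onsets in the first two weeks, and the test is essentially unchanged while onsets fall within the EAP.

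The gap would be larger (ratio 1.30) only if onsets were spread evenly to Day 29. An assumed longer symptom tail of 14 ± 14 days gives ratios of 1.18 to 1.63. These sizes rest on the protocol's 11.5 ± 5.7 days and on assumed onset patterns, entry dates and cutoff.

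Replacing the pre-specified formula would exchange a clear duration for one that mixes onset timing with illness length and gives zero to some primary events. Reporting a second, capped duration would change no conclusion. Stating in the table footnote that weeks run to resolution is ordinary reporting practice and needs no amendment.

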### 7.3. Premature Withdrawal from the Study

A subject or pediatric subject's parent/guardian has the right to withdraw from the study at any time, for any reason, and without repercussion.

The investigator and/or Sponsor have the right to withdraw a subject from the study if it is no longer in the interest of the subject to continue in the study, or if the subject's continuation in the study places the scientific outcome of the study at risk (eg, if a subject does not or cannot follow study procedures). An excessive rate of withdrawals would render the study uninterpretable; therefore, unnecessary withdrawal of subjects should be avoided.

Subjects who are withdrawn prematurely from the study will be asked to complete the ET visit, as described in Section 9.1.5.

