The study was originally planned to enroll 2000 adult and adolescent subjects. A blinded analysis of approximately 25% of enrolled subjects in this study was performed, demonstrating that higher than expected seropositivity was observed in cohort A. In addition, an unblinded administrative analyses was performed on the data based on 554 subjects to verify assumptions and adequacy of sample size. The subjects who were included in the administrative assessment will not be included in the final efficacy analysis. Thus, sample size was increased to accommodate higher seropositivity rate and the unblinded administrative assessment. The total study population was planned to be approximately 3500 adult and adolescent subjects (~3150 subjects in cohort A and ~350 subjects in cohort B) including 554 cohort A subjects in the administrative assessment and approximately 250 pediatric subjects < 12 years old (~225 subjects in cohort A1 and 25 subjects in cohort B1), with household contact exposure to individual with a confirmed SARS-CoV-2 infection.

Statistical analyses will be conducted separately in each cohort. For the purpose of the study analysis, cohorts A, A1, B, and B1 are independent. As specified earlier, the 554 subjects in the administrative assessment will not be included in the final efficacy analyses (first step analysis) however, these subjects will be included in the safety analyses. Also, the final efficacy analysis (first step analysis) will include only subjects randomized on or before January 28, 2021. The total number of subjects to be included in the first step analysis is approximately 2459. The subjects randomized after January 28, 2021 will remain blinded until the final analysis but will not be part of any formal statistical testing.

For each subject, the study comprises 3 periods: a 1-day screening/baseline period, a 1-month EAP, and a 7-month follow-up period (See [Figure 1](#)).

Figure 1: Study Flow Diagram

The schedule of events tables for this study can be found in the Appendix 10.2.

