6.3. Data Handling Convention for Missing Data

Missing data will not be imputed in listings. This section includes the methods for missing data imputation for some summary analyses, if necessary.

Date and Time of Study Treatment Injection

Since the study drug is administered at the site, the date and time of study drug administration are filled in eCRF. No missing data is expected. The information is filled in eCRF.

Adverse Event

If the severity of a TEAE is missing, it will be classified as “severe” or “Grade 3” in the frequency tables by intensity of TEAEs. If the assessment of relationship of a TEAE to the investigational product is missing, it will be classified as related to study drug.

When the partial AE date/time information does not indicate that the AE started prior to study treatment or after the TEAE period, the AE will be classified as treatment-emergent.

Medication/Procedure

If a medication date or time is missing or partially missing and it cannot be determined whether it was taken prior or concomitantly or stopped prior to the first study treatment administration, it will be considered as concomitant medication/procedure by imputing the start date on the date of first study treatment administration.

Potentially Clinically Significant Value (PCSV)

If a subject has a missing baseline value, this subject will be grouped in the category “normal/missing at baseline.”

For PCSVs with 2 conditions, one based on a change from baseline value and the other on a threshold value or a normal range, with the first condition being missing, the PCSV will be based only on the second condition.

For a PCSV defined on a threshold and/or a normal range, this PCSV will be derived using this threshold if the normal range is missing; e.g., for eosinophils the PCSV is >0.5 giga/L or $>\text{ULN}$ if $\text{ULN} \geq 0.5$ giga/L. When ULN is missing, the value 0.5 should be used.

Measurements flagged as invalid by the laboratory will not be summarized or taken into account in the computation of PCSVs.

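### Symptoms still open at the first-step analysis are closed at a study-wide cutoff, with no exception for subjects who have left, so reported symptomatic weeks can include time nobody observed

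*SAP*

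**What the plan says.** SAP 4.5.2 gives the formula: "Duration of symptomatic infection (weeks) is defined as (the end date of all symptoms minus the date of the first symptom+1)/7". It then adds one rule for unresolved symptoms. The trigger is worded "If the symptom is ongoing at the time of the first step analysis". The action that follows from this trigger is that "the end date of the symptom will be set as the cutoff date for the first step analysis". Nothing there distinguishes subjects still being followed from subjects who have left. No calendar value is given for the cutoff. The only date attached to the first step is a randomisation limit in SAP 2.1: "the final efficacy analysis (first step analysis) will include only subjects randomized on or before January 28, 2021".

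The endpoint is named "Number of weeks of symptomatic RT-qPCR confirmed SARS-CoV-2 infection (broad-term) during the EAP". It stands second among the cohort A key secondaries and is tested with the Van Elteren rank test (SAP 5.7.2 and 5.7.3). SAP 5.7.3 also promises sums: "The total weeks of infection and normalized duration (e.g., average duration infection per 1000 subjects) per treatment group will also be reported".

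No other section closes an open symptom:

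- SAP 6.2 points to 5.7.1, which deals with missing RT-qPCR results.
- SAP 5.7.3 deals with visits that lack RT-qPCR or viral load.
- SAP 6.3 opens with "This section includes the methods for missing data imputation for some summary analyses, if necessary" and then covers adverse events, medications and laboratory thresholds, but not symptom end dates.

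On leavers, Protocol 7.3 says: "Subjects who are withdrawn prematurely from the study will be asked to complete the ET visit".

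**The concern.** For a subject still in the study, the cutoff is a fair closing date, because the schedule-of-events footnotes (Protocol 9.1.1) require weekly symptom questions until resolution, also after the EAP. For a subject who withdrew, was lost or died with the symptom open, observation ended at last contact. Protocol 10.1.1 ends adverse-event follow-up at resolution or the last study visit. Read literally, the SAP counts all the time from then to the cutoff as symptomatic.

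Two subjects with the same course who leave on the same study day would therefore get different durations because they were randomised in different months. SAP 4.3 already avoids this for concomitant medications, where the period stops at the last visit of a subject who discontinues. The symptom rule has no such limit.

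At stake is the credibility of the total weeks and weeks per 1000 subjects. These sums have no protection against a few very long values.

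**Working it through.** The plan gives no expected value or power for this endpoint, so there is no stated figure to reproduce.

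**Cutoff.** The last first-step randomisation is 28 Jan 2021 (SAP 2.1), and lock follows completion of the EAP (SAP 7). Nominal Day 29 is 28 Jan + 28 days = 25 Feb 2021, ignoring the ±3-day visit window. The true cutoff may be later.

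**Unobserved credit** = cutoff − last contact. For a last contact on Day 8 (randomisation + 7 days):

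| Randomised | Last contact | Days to 25 Feb 2021 | Weeks |
|---|---|---|---|
| 28 Jan 2021 | 4 Feb 2021 | 21 | 3.0 |
| 1 Jan 2021 | 8 Jan 2021 | 48 | 6.9 |
| 1 Dec 2020 | 8 Dec 2020 | 79 | 11.3 |

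If durations were truncated at Day 29, the credit in every row would be at most (29 − 8)/7 = 3.0 weeks.

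**One illustrative subject.** Assume onset on 1 Nov 2020 and last contact on 15 Nov 2020.

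- Observed: (14 + 1)/7 = 2.1 weeks.
- Under the rule: (116 + 1)/7 = 16.7 weeks.
- Unobserved: 102/7 = 14.6 weeks.

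These dates are assumed. The first 554 or so cohort A subjects are excluded from the efficacy set (SAP 3.1 and 7), and no date is given for that boundary.

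**Share of the placebo total.** Take 1248/2 = 624 placebo subjects and assume 2-3 weeks per event.

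- Planned attack rate 10% (SAP 2.2.1): 62.4 events, 125-187 weeks; 14.6/187 = 8% to 14.6/125 = 12%.
- Administrative-assessment rate 8/223 = 3.6% (Protocol 3.2.5): 22.4 events, 45-67 weeks; 14.6/67 = 22% to 14.6/45, about 33% before rounding.

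With the mean of 11.5 days (1.64 weeks) cited in Protocol 3.2.1 instead, the shares are about 14% and 40%.

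**Effect on the comparison.** A simulation used 1000 runs, 624 subjects per arm, attack rates of 10% and 5%, and durations of 11.5 ± 5.7 days. Assumed, not from the documents: gamma-distributed durations, onset uniform over weeks 0-2, randomisation uniform over the 13 weeks before 28 Jan 2021, the share of symptomatic subjects lost with symptoms open, and an unstratified Wilcoxon test. Weeks per 1000 subjects, placebo / active (differences taken before rounding):

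| Lost with symptoms open | Closed at last contact | Closed at cutoff | Difference between arms |
|---|---|---|---|
| 2% | 163 / 81 | 181 / 90 | 82 → 91 |
| 5% | 160 / 81 | 204 / 102 | 80 → 102 |
| 10% | 156 / 78 | 242 / 123 | 78 → 119 |

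At 10% lost, the rejection rate is 0.925 with closure at last contact and 0.927 with closure at the cutoff. With equal attack rates it is 0.052 either way. The placebo-to-active ratio is 156/78 = 2.00 against 242/123 = 1.97.

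**The case against.** The best defence is that the rule applies only to a symptom known to be ongoing at the first step. A lost subject's status then is unknown, so the sentence was never meant for that subject. This reading is possible. It leaves departed subjects with no rule at all for a key secondary endpoint, and the same added sentence is needed.

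The second defence is the endpoint's name, which confines it to the EAP. If duration is truncated at Day 29, each open symptom closes no later than the subject's own Day 29. The calendar dependence goes, and the 14.6-week credit above falls to at most 2 weeks. This stands as a limit on size, so a reader should not infer that the point is the same with or without a cap. But SAP 4.5.2 writes no cap, and its formula lets even a fully followed subject exceed four weeks. That conflict with the endpoint's name needs resolving in its own right.

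Third, such subjects may be few: symptomatic subjects are questioned weekly, and leavers are asked to attend an early termination visit. The documents give 10% overall dropout but not the share lost with symptoms open, so frequency stays unknown.

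**Conclusion.** The point holds as a gap in the closing rule that affects reported magnitudes. Read literally, departed subjects gain unobserved weeks: 3.0 to 11.3 in the Day 8 examples, with the cutoff at its earliest date. Because more placebo subjects are expected to be symptomatic, the absolute difference in weeks per 1000 subjects is inflated, in the illustration from 80 to 102 if 5% of symptomatic subjects are lost with symptoms open.

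Four stronger readings are tempting and not supported:

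- That the hierarchical test is compromised. The test uses ranks, and rejection rates hardly change.
- That the relative benefit is exaggerated. The ratio between arms stays near 2.
- That 22-33% is the size of the problem. It needs the 3.6% rate; the planned rate gives 8-12%. Both need onset dates that may not occur in the analysed set.
- That cohort B is already subject to the rule. Weeks of symptoms is its first key secondary, but SAP 4.5.6 states no closing rule.

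**What to change.** Replace the sentence in SAP 4.5.2 with: *If a symptom has no end date, the end date is the earlier of the subject's last symptom assessment or contact (including early termination or death) and the first-step cutoff date.*

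In the same edit:

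- State the cutoff as a calendar date. The randomisation limit of 28 Jan 2021 cannot serve, since late-randomised subjects could then have an end date before onset.
- State whether duration is truncated at the end of the EAP, so that formula and endpoint name agree.
- State that the rule covers the other weeks-of-symptoms endpoints, including cohort B.
- Report by arm how many durations were closed this way.

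The cost is a few sentences and a small programming change, using visit and contact dates the study should already hold. The drawback is that closing at last contact understates duration for subjects who left while ill; the reported counts make that visible.
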